# CHAPTER I

## INTRODUCTION

Musculoskeletal conditions are one of the most prevalent and costly disorders globally (**Murray et al., 2012**), with shoulder pain being the third most common cause of musculoskeletal consultation in physiotherapy setting (**Kooijman et al., 2013**). The annual incidence of shoulder complaints is estimated to at 29.3 per 1000 a year and its prevalence in the general population is estimated between 41% and 48% (**Greving et al., 2012**).

Sub-acromial Impingement Syndrome (SIS) has been identified with a prevalence of almost 40% among shoulder pathologies (**Aceituno-Gómez et al., 2019**). SIS has significant economic consequences owing to its treatment costs and losses incurred through workplace absenteeism (**Virta et al., 2012; Hopkins et al., 2016**).

Intrinsic and extrinsic factors that contribute to the development of SIS include Inflammation in the supra humeral space, inhibition of the rotator cuff muscles, degeneration of the rotator cuff tendons, abnormal scapular position and kinematics (**Escamilla et al., 2014**) and altered kinematics. Currently SIS covers a range of pathologies from subacromial bursitis to rotator cuff tendinopathy and full-thickness rotator cuff tears (**Lewis, 2009; Harrison and Flatow, 2011**).

Altered scapular motion that occurs during active shoulder movements is referred to as scapular-thoracic dyskinesia (**Kibler et al., 2009, 2013**). It presents itself by diversified scapular motion resulting in a functional instability in activities involving arm elevation (**Jobe et al., 1989; Kibler et al., 2009, 2013**). Dyskinesia

might increase the risk of developing shoulder pain by 43% (**Hickey et al., 2018**), and simultaneously it appears to be a non-specific response to various shoulder dysfunctions, since no specific pattern of dyskinesia is associated with a specific diagnosis (**Ginn and Cohen, 2005**).

In patients diagnosed with rotator cuff tendinopathy, intermuscular coordination between the lower trapezius and serratus anterior, as well as between the lower trapezius and upper trapezius is disrupted in arm elevation tasks, indicating two altered ratios and the importance of the muscle function (**Michener et al., 2016**). Alterations in scapular muscle performance have been found in subjects with scapular dyskinesia. Hyperactivity of the upper trapezius (UT) with reduced middle (MT) and lower trapezius (LT) muscle activation in addition to insufficient serratus anterior (SA) muscle function have been related to decreased amounts of scapular upward rotation, external rotation, and posterior tilt in patients (**Ludewig et al., 2010**).

Research into scapular stability exercises for the management of SIS is increasing, yet there is little evidence on their efficacy (**Ginn and Cohen, 2005**). Interventions focused on reducing scapular dyskinesia compared to just stretching and strengthening exercises result in significantly better shoulder disability measures (**Moura et al., 2016; Struyf et al., 2013**). The addition of scapular stabilization exercises to stretching and strengthening exercises can be significantly beneficial in increasing the strength, developing joint position sense and decreasing dyskinesia (**Baskurt et al., 2011**).

Proprioceptive neuromuscular facilitation (PNF) is a rehabilitation concept which is widely used by physical therapists (**Westwater-Wood et al., 2010; Smedes et al., 2016**), promoting motor learning, motor control, strength and mobility

(IPNFA, 2019; Smedes et al., 2016). This comprehensive rehabilitation approach includes task-oriented training with manual facilitation aimed at motor learning and motor control (Adlers et al., 2014; Smedes et al., 2016). Also, PNF positions improve movement efficiency of the joint by inducing changes in the muscle activation sequence (Shimura and Kasai, 2002) and it reportedly helps in the early recovery of the patients with SIS (Nakra et al., 2013).

To the authors' knowledge, none of the studies has investigated the potential effect abnormal scapular muscle strengthening versus PNF exercise on the muscle strength, muscle ratio, and ROM of the scapula during arm elevation in patient with SIS.

### **Purpose of the study:**

The purpose of this study is to compare the effect of scapular muscle strengthening versus PNF exercise on scapular muscle strength, scapular muscles ratio, scapular asymmetry, pain, and function in patients with shoulder impingement syndrome.

### **Statement of the problem:**

Shoulder pain and dysfunction are common complaints among individuals seeking care from physical medicine and rehabilitation specialists. Recently, clinicians and investigators have focused increased attention on the role of the scapula in the pathogenesis of shoulder pain in general and impingement symptoms in particular.

### **Research question:**

What is/are the effect(s) of scapular muscle strengthening compared to PNF exercise on isometric scapular muscle strength, scapular muscles ratio and scapular asymmetry in patients with shoulder impingent syndrome.

### **Significance of the study:**

Shoulder impingement syndrome (SIS) is a common cause of shoulder pain. Shoulder pain is highly prevalent within the general population, second to lower back pain. Studies suggest that SIS is the most common cause of shoulder pain, accounting for approximately 30–35% among the shoulder disorders (**Faber et al., 2006; Michener et al., 2004; Natvig & Juel, 2014**)

Shoulder complaints have an unfavorable outcome; only about 50% of all new episodes presented in the primary care setting show complete recovery within six months, and one year after the first consultation, 40-50% of patients report that their symptoms have persisted or recurred (**Lewis, 2009**).

SIS results in functional limitations which significantly interfere with the subject's quality of life (**Aceituno-Gómez et al., 2019**). Thus, shoulder pain induced by SIS is widespread and imposes a considerable burden on the affected person and society.

There is evidence which demonstrated that motor control and strengthening exercises can improve function in shoulder impingement patients; but the evidence is limited to a small sample single-subject study design. Realignment the scapula can change muscle recruitment patterns in patients with neck pain, but this has yet to be shown in shoulder pain (**Roy et al., 2009**)

An increasing number of studies have correlated abnormalities in scapular position and motion (dyskinesia) with impingement symptoms, rotator cuff dysfunction, and instability (**Hallström & Kärrholm, 2006; Ludewig & Cook, 2000b; McClure et al., 2006**), however, till the author knowledge no study attempted to study scapular muscle training versus scapular PNF exercise in patients with shoulder impingement syndrome.

In view of the new insights and research findings on the role of the scapula in shoulder pathologic abnormality, current exercise protocols emphasize the importance of scapular muscle training as an essential component of shoulder rehabilitation (**Bang & Deyle, 2000; Burkhart et al., 2003; Hintermeister et al., 1998**). Restoration of muscle control and balanced coactivation in particular is a challenge to the clinician (**Cools, Dewitte, et al., 2007**).

Previous data were obtained from a group of young, healthy subjects with no history of shoulder impairment (**McClure et al., 2006**). On the basis of their results, we cannot conclude that patients suffering from shoulder pain or local muscle imbalances will show similar muscle balance ratios performing these exercises.

Our study may be considered as a first step in the investigation of rehabilitation exercises for the restoration of normal scapular muscle strength, scapular muscles ratio, scapular asymmetry, pain, and function in patients with SIS.

### **Hypotheses of the study:**

1. There will be no significant difference between scapular muscle strengthening and PNF exercise on improving muscle strength of upper trapezius in patients with shoulder impingement syndrome.

2. There will be no significant difference between scapular muscle strengthening and PNF exercise on improving muscle strength of middle trapezius in patients with shoulder impingement syndrome.
3. There will be no significant difference between scapular muscle strengthening and PNF exercise on improving muscle strength of lower trapezius in patients with shoulder impingement syndrome.
4. There will be no significant difference between scapular muscle strengthening and PNF exercise on improving muscle strength of serratus anterior in patients with shoulder impingement syndrome.
5. There will be no significant difference between scapular muscle strengthening and PNF exercise on muscle ratio of upper trapezius/lower trapezius muscles in patients with shoulder impingement syndrome.
6. There will be no significant difference between scapular muscle strengthening and PNF exercise on muscle ratio of upper trapezius/middle trapezius muscles in patients with shoulder impingement syndrome.
7. There will be no significant difference between scapular muscle strengthening and PNF exercise on muscle ratio of upper trapezius/serratus anterior muscles in patients with shoulder impingement syndrome.
8. There will be no significant difference between scapular muscle strengthening and PNF exercise on scapular symmetry at 0° abduction in patients with shoulder impingement syndrome.
9. There will be no significant difference between scapular muscle strengthening and motor control exercise on scapular symmetry at 45° abduction in patients with shoulder impingement syndrome.
10. There will be no significant difference between Scapular muscle strengthening and motor control exercise on scapular symmetry at 90° abduction in patients with shoulder impingement syndrome.

11. There will be no significant difference between scapular muscle strengthening and PNF exercise on improving pain in patients with shoulder impingement syndrome.
12. There will be no significant difference between scapular muscle strengthening and PNF exercise on improving function in patients with shoulder impingement syndrome.

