## Sample size calculation:

In order to detect an effect size of Cohen's  $d = 0.80$  with 80% power ( $\alpha = 0.05$ ), G\*power software (version 3.1.9.7; Franz Faul, Universitat Kiel, Germany) suggests we will need 64 participants, however, we will aim to recruit 66 subjects to have equal groups representation (22 per group) using analysis of variance (ANOVA) test as shown in the (figure 7).

[figure not shown]

Figure 1 ample size calculation

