## **Shoulder pain and disability index (Appendix II):**

Self-report questionnaire developed to measure the pain and disability associated with shoulder pathology. The SPADI consists of 13 items in two subscales: pain (five items) and disability (eight items).

The pain dimension consists of five questions regarding the severity of an individual's pain. Functional activities are assessed with eight questions designed to measure the degree of difficulty an individual has with various activities of daily living that require upper-extremity use. The SPADI takes 5 to 10 minutes for a patient to complete and is the only reliable and valid region-specific measure for the shoulder **(Roash al., 1991)**.

Patients asked to mark the appropriate point on the scoring system of the questionnaire, which represented their status of shoulder pain and disability. Total pain score:  $/ 50 \times 100 = \%$ , Total disability score:  $/ 80 \times 100 = \%$  and Total SPADI score:  $/ 130 \times 100 = \%$  Higher score on the SPADI is indicative of higher pain and/or disability **(Breckenridge al., 2011)**.

Psychometric Properties the SPADI :MDC: 18 point (MDC 95%) with  $ICC \geq 0.89$ , The MCID has been reported to be 8 points; this represents the smallest detectable change that is important to the patient **(Paul et al 2004)**.

No large floor or ceiling effects for the SPADI have been observed **(Bot et al 2004, Roy et al 2009)**.

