**Figure 20 SCAPULAR ANTERIOR DEPRESSION**

## **Statistical analysis**

- Data will be analyzed using the statistical package for social science (SPSS) program, version 27 (SPSS Inc, Chicago, IL, USA).
- Descriptive statistics will be used to summarize the data. Data will be reported as mean  $\pm$  SD for quantitative variables and frequency distribution (%) for categorical variables.
- The normality of data will be checked using Shapiro–Wilk test.
- Levene’s test will be used to check the homogeneity between groups.
- Two-way Multiple Analysis of Variance (MANOVA) will be conducted to compare the mean values of the measured variables of the three groups.
- The level of significance for all statistical tests will be set at  $\alpha = 0.05$ .

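### All twelve hypotheses are unlabelled predictions of non-significance without alternatives, and the planned three-group MANOVA gives no estimate of the difference between the two exercises that they concern

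*Protocol*

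**What the plan says.** The Protocol, under 'Hypotheses of the study', lists twelve items on strength, muscle ratios, scapular symmetry, pain and function. All take the same form; the pain item reads "There will be no significant difference between scapular muscle strengthening and PNF exercise on improving pain in patients with shoulder impingement syndrome". The list is not labelled as null hypotheses, and no alternative or margin is given. Items 9 and 10 name motor control exercise, which is not one of the three arms, in place of PNF; these need to be reconciled with the arms.

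The stated aim is neutral: "The purpose of this study is to compare the effect of scapular muscle strengthening versus PNF exercise".

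The trial is sized as a test of difference. For d = 0.80 and 80% power, 'Sample size calculation' states that "we will need 64 participants" and that "we will aim to recruit 66 subjects to have equal groups representation (22 per group"), "using analysis of variance (ANOVA) test".

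Under 'Statistical analysis' the only comparison is: "Two-way Multiple Analysis of Variance (MANOVA) will be conducted to compare the mean values of the measured variables of the three groups". The decision criterion is: "The level of significance for all statistical tests will be set at" 0.05. Group C, which receives no treatment, is one of the three groups.

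The SPADI section gives an MDC95 of 18 points with an ICC of at least 0.89, and says "The MCID has been reported to be 8 points". That MCID is used in neither the sample size nor the analysis. No MCID is given for strength, ratios or symmetry.

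**The concern.** Each item predicts the outcome of a test rather than stating something about the population means. With no label and no alternative, a reader can take p > 0.05 as fulfilling the hypothesis, and the noisier the data, the more easily that happens.

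The analysis does not close the gap. Every hypothesis is about the two exercise arms, but the MANOVA is an omnibus test over three arms. A significant result could come entirely from the untreated arm and would not show that A and B differ. A non-significant result would come without an A-B estimate or interval to show how large a difference remains possible. In either case the trial's own question is left without a direct answer.

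**Working it through.** **Inputs.** From the protocol: 22 per arm, alpha 0.05, d = 0.80, 80% power, SPADI MCID 8 points, MDC95 18 points, ICC 0.89 (its stated lower bound). Assumed: the SPADI SD, which the protocol does not give; the pre-post correlation r; and that the 8 points and the derived SD apply to the pain and disability subscales as well as the total.

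**Step 1: the plan's own figure.** Taking f = d/2 = 0.40 in a one-way ANOVA with three groups, 64 is the smallest total N with at least 80% power (63 gives 0.798, 64 gives 0.805, 66 gives 0.818). The stated 64 therefore reproduces as an omnibus test of difference. For the comparison that the hypotheses name, 22 v 22 by two-sided t test, power at d = 0.80 is 73.6%.

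**Step 2: SD implied by the protocol.**
- SEM = 18 / (1.96 × √2) = 6.49 points.
- SD = 6.49 / √(1 − 0.89) = 19.6 points. A higher ICC gives a larger SD.

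**Step 3: precision of A minus B.**
- Half-width of the 95% CI = t(0.975, 42) × √(2/22) × SD = 0.608 × SD.
- At SD 19.6 this is 11.9 points.
- With baseline adjustment, multiply by √(1 − r²): 11.9 × 0.866 = 10.3 at r = 0.5, and 11.9 × 0.714 = 8.5 at r = 0.7.
- The half-width equals 8 points at SD = 8 / 0.608, about 13. Above that, even an observed difference of zero would typically not exclude 8 points.

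**Step 4: chance of p > 0.05 when the true difference is 8 points** (noncentral t, 22 per arm).

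| SD (points) | d = 8/SD | Power | Non-significant |
|---|---|---|---|
| 10 | 0.80 | 74% | 26% |
| 15 | 0.53 | 41% | 59% |
| 19.6 (derived) | 0.41 | 26% | 74% |
| 25 | 0.32 | 18% | 82% |
| 17.0 (19.6 adjusted, r = 0.5) | 0.47 | 33% | 67% |
| 14.0 (19.6 adjusted, r = 0.7) | 0.57 | 46% | 54% |

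**Step 5: chance that the whole 95% CI lies within −8 to +8 when the true difference is zero** (simulation, 22 per arm). This is 47% at SD 10, about 1% at SD 15 and below 0.1% at SD 20.

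**The case against.** The strongest reply is that this is the conventional way to write a null hypothesis. The aim is to compare, the trial is sized to detect an effect, and the analysis compares means. Nowhere does the protocol claim equivalence or non-inferiority, or say that p > 0.05 confirms anything. This stands. A reader might infer that the trial is set up to declare the two programmes equally effective from a non-significant test; the documents do not say so.

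A reader might also carry the MCID consequence across all twelve hypotheses. That is not supported either: the 8 points belong to the SPADI, so the argument covers items 11 and 12 only, and applying it to the subscales is itself an assumption. For items 1 to 10 only the wording and the missing contrast can be criticised.

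The 74% is also fragile. It rests on a derived SD and on an unadjusted two-sample test that the protocol does not name, whereas outcomes are measured before and after treatment. Under a very favourable assumption, change scores with a pre-post correlation of 0.89, the SD falls to 9.2, the half-width to 5.6 points and the non-significant share to 19%. That correlation would have to equal the quoted reliability coefficient across six weeks of treatment.

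Last, intervals and rules for interpretation may sit in a statistical analysis plan that is not shown, so their absence alone is not the point. What the protocol itself fixes badly is hypotheses about A versus B with neither label nor alternative, paired with an omnibus test that does not address A versus B.

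**Conclusion.** The point holds as a defect of wording and of fit between hypotheses and analysis. All twelve items are open to being upheld by non-significance, and the analysis as stated yields no A-B estimate. It does not hold as a claim that the protocol plans to infer equality.

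For SPADI the practical size is considerable but uncertain. At the derived SD, a true difference of one MCID would more often than not be non-significant, with or without baseline adjustment at r = 0.5 to 0.7. At an SD of 10 the reverse is true. The result depends on the derived SD, the assumed r, use of the 8 points for the subscales, and no loss of participants from the 22 per arm.

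**What to change.** 1. Label each item as a two-sided null (A and B have equal means) and give its alternative (they differ). Reconcile items 9 and 10 with the arms.
2. For each outcome, add a baseline-adjusted A-B contrast with its 95% CI, for example ANCOVA on the post-treatment value.
3. State that a non-significant result is not evidence of equal effect.
4. For SPADI, read the CI against the 8-point MCID and call a non-significant result inconclusive if the interval reaches 8 points or more in either direction. This is an aid to interpretation, not a success criterion. At 22 per arm the answer will usually be inconclusive unless the (adjusted) SD is below about 13 points; even at SD 10 with no true difference, the interval lies inside ±8 only about half the time.

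Cost: one added model on data already collected, no extra participants, and a less favourable description of a neutral result.

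If equivalence is in fact intended, a justified margin and a new sample size are needed. With 8 points as an illustrative margin, two one-sided tests at 0.05 with 80% power and a true difference of zero need 2 × (SD × (1.645 + 1.282) / 8)² per arm: about 103 at SD 19.6 (27 at SD 10, 61 at SD 15, 168 at SD 25).

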### **Delimitation:**

This study will be delimited to the following:

### **Subjects:**

1. sixty-six Male and female subjects with SIS and age between 20-50 (Cools et al., 2012).
2. body mass index (BMI) < 20 kg/m^2 (Celik et al., 2012).
3. subjects complaining secondary shoulder impingement (Cools et al., 2012).
4. subjects with altered scapular resting positions and dyskinesia (Cools et al., 2007; 2003).

### **The instrumentations will be limited to:**

1. Hand-held dynamometer.
2. Isometric strength imbalance of shoulder girdle muscles.
3. Modified Lateral Scapular Slide test.
4. shoulder pain and disability index (SPADI).

### **The intervention will be limited to:**

1. Scapular muscle strengthening exercise
2. Proprioceptive neuromuscular facilitation (PNF)

### **Basic assumption:**

It will be assumed that:

- All the subjects will be co-operative and honest in answering the questions
- All the participants will be evaluated under the same conditions.

### **Definition of terms:**

#### **Proprioceptive neuromuscular facilitation (PNF)**

Is an exercise modality defined to facilitate the responses of neuromuscular mechanism by stimulating proprioceptors. Effect mechanisms of PNF techniques are stimulating postural reflexes using gravity force to facilitate muscles, using eccentric contractions for muscle activation and utilizing diagonal movement patterns in activation of bi-articular muscles (**ahimura et al., 2002**).

#### **Shoulder impingement**

Impingement syndrome was first defined by Charles Neer in 1972, described as the tightness of the soft tissues under the acromion that compromise its functionality (**Neer, 1972**).

Shoulder impingement represents mechanical compression of the rotator cuff tendons and subacromial bursa against the anteroinferior undersurface of the acromion and coracoacromial ligament especially during elevation of Several kinematic changes are present in people with symptoms of impingement which

results in further decrease in the available supraspinatus muscle outlet or supra humeral space (**Chilgar et al., 2020**).

## **Primary and Secondary shoulder impingement**

Primary shoulder impingement occurs when the rotator cuff tendons, long head of the bicep's tendon, glenohumeral joint capsule, and/or the subacromial bursa become impinged between the humeral head and the anterior acromion. Secondary shoulder impingement is defined as a relative decrease in the subacromial space due to glenohumeral joint instability or abnormal scapulothoracic kinematics (**Kachingwwe et al, 2008**).

## **Scapular dyskinesis**

Scapular Dyskinesis Dyskinesis (dys [alteration of] kinesis [motion]) is a general term that is used to describe loss of control of normal scapular physiology, mechanics, and motion. The term dyskinesia is often used interchangeably with dyskinesis (**Kibler et al., 2012**).

## **CHAPTER III**

### **Subjects, Materials and methods**

This study will be conducted in EL KARNAK international hospital, Luxor, Egypt, to compare the effect of scapular muscle strengthening versus PNF exercise on scapular muscle strength, scapular muscle ratio, scapular asymmetry, pain, and function in patients with shoulder impingement syndrome. The study is estimated to run between April 2022 to April 2023 after obtaining the ethical committee approval.

